- Currently prescribed ART
- Planning on remaining a resident of Cape Town for at least 6 months postpartum
- Able to provide informed consent for research including:
 - Willingness to be randomly allocated to the Transition intervention or enhanced standard of care
 - Consent to have study personnel access medical records under confidential conditions and for the purposes of the study only
 - Consent to other study procedures, including follow-up for at least 6 months
 - Ability to speak isiXhosa or English

Note: no restrictions will be made based on timing of HIV diagnosis or prior exposure to ART.

Exclusion criteria include:

- Failure to meet any of the inclusion criteria
- Significant pre-existing psychiatric comorbidity at enrolment that may impact ability to consent according to the judgement of study personnel (including cognitive impairment or known psychotic disorder)

Note: mothers will not be withdrawn from the study following foetal complications or death

5. Recruitment

Women attending the Gugulethu MOU who have documented HIV infection and clinical indication of pregnancy according to a provider will be told about the study by staff at the MOU. If women express interest in the study, they will be asked to approach study staff. Study staff will provide basic information about the study, and women who are interested in participating will be screened based on the inclusion/exclusion criteria detailed above. Women who are eligible will undertake the informed consent process described below. Study staff will emphasize that all study activities are entirely separate from routine antenatal/postpartum and HIV care and that refusal or withdrawal from the study will have no impact on their ability to access any of these services.

6. Study Arms

Open Pilot

All women recruited for the open pilot (n=5) will receive the Transition intervention (see below). All open pilot participants will receive 4 monthly one-on-one meetings with the community

health worker. As a reminder the purpose of the open pilot is to pretest all study procedures, particularly recruitment and retention, to increase the feasibility of the RCT, as well as to pilot test the intervention content. Participants will fill out end of session questionnaires that inquire about specific content and design features of the intervention. This information will guide the next iteration of the intervention to be tested in the small-scale RCT.

Randomized Controlled Trial Study Arms

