Our team has extensive experience in utilizing data from routinely collected electronic medical records in this setting, including for ART and PMTCT outcome assessment.^{60,61} Data will be requested from the Western Cape Provincial Data Centre, and we will use participants' provincial folder number (requested as part of tracing information) to facilitate an accurate electronic data request. Permission to review electronic clinical records of participants will be included in informed consent documents. Following standard procedures, we will request approval from the Provincial Department of Health to access electronic medical records. Established procedures are in place to ensure patient confidentiality. The project manager will link these data to participants' unique participant identifiers.

For the primary outcomes obtained from routine medical records (engagement in care and HIV viral suppression), we will use the following definitions:

- Engagement in care will be classified as any evidence of engagement in routine HIV services, including evidence of: HIV visit attendance; ART collection at a pharmacy; laboratory testing of HIV viral load or CD4 cell count
- HIV viral suppression will be classified as a viral load <200 copies/mL

For the primary outcome, we will use a window of up to 3 months around the 6-month postpartum study visit. In cases where there is evidence of multiple HIV viral load results in this window, we will use the result closest to the 6-month postpartum study visit for the primary outcome. For women who are lost to follow-up, we will use the median time of visits attended among those who are retained at study measurement visits to assess engagement in care and HIV viral suppression. As the primary outcome data will come from routine medical records, all women will have outcome data regardless of retention at study measurement visits.

Routinely collected clinical data will be linked with the written permission of (a) the participant (via informed consent), (b) the research oversight body of the Provincial Government of the Western Cape including the Provincial Data Centre, and (c) the HREC. Established procedures are in place to ensure patient confidentiality.

Aim 3 Qualitative Component

In-depth interviews will be conducted with participants randomized to the intervention condition (n=up to 30) after the completion of follow-ups in order to assess participants' experiences of the

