Quantitative data will be captured into a custom designed Microsoft Access database. The database will be password-protected following standard password safety procedures, and will be maintained in a firewall-protected UCT server with daily backups. The database will be designed and maintained by the project manager. The study coordinator will direct queries and data

quality assurance (QA)/quality control (QC) activities, and supervise data entry, with oversight from the project manager. Data QA will be in the form of robust database structure and platform, and 'front-end' data checks including real-time database queries. QC will be through data checking scripts to identify out-of-range values, logic violations and missing observations. Queries will be resolved based on reference to the completed questionnaires in question; all data queries and responses will be logged, and edits will be implemented through separate program files.

Qualitative data from IDI will be transcribed verbatim and translated into English. Translations will use unique participant identifiers, not participant names. All electronic files will be encrypted and password protected.

Data analysis

Quantitative data will be exported to Stata Version 14.0 (Stata Corporation, College Station, Texas) for analysis. We will analyze all primary and secondary outcomes preliminarily using simple means and standard deviations and point-biserial correlations to estimate effect sizes where appropriate. For outcomes that are indicative of a possible difference by condition, we will utilize more advanced analytic techniques, i.e generalized estimating equations (GEE), as follows:

To compare the impact of intervention condition on self-reported ART adherence, engagement in ART services and HIV viral suppression, we will utilize a series of generalized estimating equations (GEE) using Poisson distributions where appropriate. Outcome analyses will control for baseline self-reported adherence and any baseline differences on demographic variables. Intervention condition, time of assessment, and condition*time interaction will be entered as model effects. We will use GEEs to predict key psychosocial outcomes (adherence self-efficacy) by intervention condition. If there is evidence of an intervention effect we will explore factors that may modify intervention effects, we will compare intervention effects within subgroups of women based on key demographic clinical and psychosocial characteristics.

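### The GEE models choose demographic covariates by observed imbalance and name no own-baseline covariate for adherence self-efficacy or viral suppression

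*Combined protocol and SAP*

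**What the plan says.** Section 9 (Data analysis) works in two stages. The first uses "simple means and standard deviations and point-biserial correlations to estimate effect sizes where appropriate". The second is conditional: "For outcomes that are indicative of a possible difference by condition, we will utilize more advanced analytic techniques", meaning GEE.

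The GEE models are introduced with the words "To compare the impact of intervention condition on self-reported ART adherence, engagement in ART services and HIV viral suppression". The adjustment rule follows: "Outcome analyses will control for baseline self-reported adherence and any baseline differences on demographic variables". Then: "Intervention condition, time of assessment, and condition*time interaction will be entered as model effects". Self-efficacy has its own sentence, with no covariates: "We will use GEEs to predict key psychosocial outcomes (adherence self-efficacy) by intervention condition".

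Other sections bear on this:

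- **Section 2** defines preliminary efficacy for adherence, retention and viral suppression as the correlation of each with study arm at 6 months postpartum.
- **Section 4** requires a current ART prescription and consent to record access, and adds that "no restrictions will be made based on timing of HIV diagnosis or prior exposure to ART".
- **Section 7, measures table**, marks self-efficacy and self-reported adherence at enrolment, 3 months and 6 months. Viral load carries no enrolment mark, though the table may be damaged.
- **Section 7, record linkage**: "Data will be requested from the Western Cape Provincial Data Centre". It defines a window only around the 6-month visit.
- **Section 7, Randomization**, describes 1:1 allocation by envelope and mentions no stratification.
- **The Protocol Summary** reports 43 women randomised.

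**The concern.** Two things look wrong.

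First, the demographic clause has no variable list, test or threshold. The model is therefore undefined until someone looks at the data by arm. The size of a chance difference also says nothing about whether the variable predicts the outcome, so the rule can spend degrees of freedom on irrelevant variables and omit prognostic ones that happen to balance.

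Second, an outcome's own earlier value is often its best predictor. None is named for self-efficacy, where it is already collected. None is named for viral suppression, where women may be newly started or long established on ART and so may differ in viral control at entry.

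Section 9 says that the pilot is meant to yield an effect size and a direction to support a larger trial. With 43 women and no stratification mentioned, chance imbalance in a prognostic baseline feeds into that estimate, and residual variance that could be removed stays in.

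**Working it through.** **1. The plan's own figure.** Section 9 states power of 29%, 65% and 98% for d = 0.30, 0.50 and 0.80 with 60 women, two follow-ups and baseline adherence as a covariate. It gives no correlation, so the figure cannot be strictly reproduced. A plain two-sided two-sample test with 30 per arm gives 21%, 49% and 87%. Multiplying the variance by 1 − r² with r = 0.58 (one follow-up) gives 30%, 66% and 97%. Averaging two follow-ups without baseline, factor (1 + r)/2 with r = 0.28, gives the same rounded values. So the power figures do not identify a baseline correlation, and they say nothing about suppression or self-efficacy.

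**2. Which outcomes are affected.**

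- Self-reported adherence: the named covariate is the baseline of the same construct. Only the instrument is open. Section 2 scores a three-item scale from 0 to 100; the measures table lists a team tool and a visual analog scale.
- Engagement: all women are recruited in antenatal care with integrated HIV services and are prescribed ART, so there is almost nothing to adjust for.
- Viral suppression: no earlier viral load is named.
- Self-efficacy: the covariates are unstated.

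**3. Precision.** Take a single follow-up, a continuous outcome with variance 1, and N = 43. The correlations are assumed. SE = √[(4/43)(1 − r²)].

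| Covariate | SE | Variance cut | Power at d = 0.5 |
|---|---|---|---|
| Unrelated to outcome (r = 0) | 0.305 | – | 37% |
| Own baseline, r = 0.3 | 0.291 | 9% | 41% |
| Own baseline, r = 0.5 | 0.264 | 25% | 47% |

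If baseline adherence already correlates 0.3 with the outcome, the fair comparison is 1 − (1 − r²)/(1 − 0.09):

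- r = 0.3: 1 − 0.91/0.91 = 0%.
- r = 0.5: 1 − 0.75/0.91 = 18%.
- r = 0.2: 1 − 0.96/0.91 = −5%, a small loss.

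**4. Chance imbalance in baseline suppression.** Assume a 21/22 split and a proportion p suppressed at entry. SD = √[p(1 − p)(1/21 + 1/22)], which gives 14.0, 12.2 and 9.2 points for p = 0.7, 0.8 and 0.9. That is imbalance in the covariate. With equal variances, the shift in the estimated effect is r times the imbalance: 0.3 × 12.2 = 3.7 and 0.5 × 12.2 = 6.1, so roughly 4-6 points.

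**5. The same for a continuous baseline such as self-efficacy.** The SD of the between-arm difference is √(4/43) = 0.305 SD units. A one-SD imbalance shifts an unadjusted estimate by 0.3 × 0.305 = 0.09 to 0.5 × 0.305 = 0.15 SD. The chance of an imbalance above 0.5 SD is about 10%.

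**6. Cost of the viral load covariate.** Three categories use two degrees of freedom. The approximate variance inflation is (43 − 3)/(43 − 3 − 2) = 40/38 = 1.05, or 5%.

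**The case against.** The strongest reply is that the gain may be small and may not reach the headline results. The section 2 estimates and the first-stage screen are unadjusted, and GEE is run only for outcomes that look different there. Better covariates in a conditional second stage leave the main correlations unchanged. This stands, and the fix has to include reporting the adjusted model for every outcome.

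For viral load, no enrolment value is scheduled, and how many women have an earlier result on record is unknown. In newly started women that result may predate ART and predict less well. The two degrees of freedom offset about half of a 9% gain. This stands too, and it makes that part conditional on what the records hold.

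It can also be said that if enrolment is one of the GEE time levels, the baseline self-efficacy score already enters as a repeated outcome. The plan does not say. The power statement counts two follow-ups and controls for baseline adherence, which suggests that enrolment is a covariate and not a time level. Even if it were a level, this would not help suppression, for which no enrolment value is scheduled.

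A reader might infer that every outcome model ignores its own baseline. The documents do not support that: the adherence model adjusts for baseline adherence, and engagement has no useful baseline. Nor do they show that the enrolment self-efficacy score is excluded, only that it is not named.

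Finally, section 9 openly calls the pilot exploratory and underpowered. That tempers the importance, but it does not justify choosing covariates after seeing the arms.

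**Conclusion.** The point holds for the demographic clause, for self-efficacy and, conditionally, for viral suppression. The objection to selecting demographics by imbalance needs no assumed number: the rule is driven by the data and is not pre-specified.

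The precision gain is modest and uncertain. It ranges from nothing to about a quarter of the variance over assumed correlations of 0.3-0.5, depending on how much baseline adherence already explains. It could be slightly negative if the own-baseline correlation were only 0.2. The linear formula is only a rough guide for a binary outcome such as suppression.

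A reader might take the 12-point SD of baseline suppression imbalance as a possible 12-point error in the treatment effect. It is not. Under the same assumptions (80% suppressed at entry, r = 0.3-0.5), a one-SD imbalance moves the estimate by roughly 4-6 points.

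**What to change.** Before anyone sees data by arm, state the covariates for each outcome in section 9:

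1. Delete the clause on baseline demographic differences, or replace it with a short list of prognostic variables fixed in advance. Cost: wording.
2. Self-efficacy model: adjust for the enrolment self-efficacy score. It is already collected, so this is free.
3. Viral suppression model: adjust for the last viral load on record before randomisation (below 200, 200 or above, none on record), if the provincial extract holds enough earlier results. Cost: an earlier start date on the record request and up to two degrees of freedom in 43 women.
4. Self-reported adherence model: use the enrolment score on the same scale as the outcome, and name that scale. Cost: wording, provided that scale is the one administered at enrolment.
5. Engagement: no own-baseline covariate.
6. Report the adjusted estimate for each outcome beside the unadjusted correlation, whether or not the first-stage screen suggests a difference. State whether enrolment is a GEE time level or a covariate.

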Study Protocol

Adherence to HIV Treatment Postpartum: The Implications of Transitions Among Women Living with HIV in South Africa

ClinicalTrials.gov #: NCT04846569

Version 5.0

November 5, 2021

IRB Federalwide Assurance Numbers:

- FWA00004460 (Brown University)
- FWA00001637 (University of Cape Town)

Study Sponsor: National Institute of Mental Health (K01MH112443)

Protocol Summary

Adherence to HIV Treatment Postpartum: The Implications of Transitions Among Women Living with HIV in South Africa

Study Aims:

Aim 1: Identify contextual, interpersonal, clinic, and individual-level factors that influence women's HIV treatment adherence during periods of key points of transition during pregnancy and postpartum, using longitudinal in-depth qualitative interviews among a cohort of pregnant women (N=25-30) following them up to 12 months postpartum.

Aim 2: Evaluate the feasibility and preliminary efficacy of a Transition Theory-based ART adherence intervention for postpartum women living with HIV, using a small scale randomized controlled trial (RCT; N=60).

Aim 3: Assess participants' experiences of the intervention, perceived usefulness, and identify ways to refine the intervention for future evaluation, using in-depth individual interviews will be conducted with all participants in the intervention condition after follow-up assessments have been completed.

Sample size for RCT: 62 participants consented; 43 randomized

Study population: Adult (≥ 18 years), HIV-positive, pregnant (23-34 weeks) women attending antenatal services at the study site, prescribed ARVs

Participating site: Gugulethu Midwife Obstetric Unit, Cape Town, South Africa

Study design: Small-scale two-arm randomized control trial, assessing feasibility and preliminary efficacy.

Study timeline for RCT: April 2021-December 2022

Principal Investigator:

[name]
Assistant Professor of Behavioral and Social Sciences
International Health Institute
Brown University School of Public Health
[name]
[name]
[name]
[contact]

Co-Investigators/K01 Mentors:

[name], PhD

Professor of Epidemiology and Biostatistics
School of Public Health and Family Medicine
University of Cape Town
Cape Town, South Africa
[name]
[contact]

[name]
Professor, Behavioral and Social Sciences
Brown University School of Public Health
[name]
[name]
[contact]
[contact]

[name]
Associate Professor, Epidemiology

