Sample size considerations: pilot study

The overall goal of this pilot study is to determine feasibility and potential efficacy to support future larger, fully-powered tests of the intervention's efficacy. We fully acknowledge the exploratory nature of this pilot. With a sample size of 60, between two groups, 2 follow-up measurements, controlling for self-reported baseline adherence, $p=0.05$, we will have 29% power of finding a small effect (Cohen's $d=0.30$), 65% power of finding a moderate effect ($d=0.50$), and 98% power of finding a large effect ($d=0.80$). This study will be underpowered to find significant small and moderate effects however, we will be able to calculate an effect size and the direction of its impact to support a larger scale test of the intervention.

The facility that is participating in this study, the Gugulethu MOU, sees approximately 4800 pregnant and postpartum women annually, with an antenatal HIV prevalence of 28%. Thus, we do not anticipate difficulty recruiting this sample within the allotted timeframe.

Sample size considerations: In-depth Interviews (Aim 3)

We propose to interview all of the women randomized to the intervention condition ($n=$ up to 30). Based on our follow-up rates for the longitudinal qualitative cohort (HREC 344/2017), we anticipate at least an 80% retention rate at 6 months postpartum, which equates to an anticipated 24 participants completing in-depth interviews. Based on our previous experiences working with this population, we feel that 24 participants will be enough to reach saturation on key themes related to acceptability of the intervention.

Data management

The study includes data from four sources: (1) interviewer-administered questionnaires; (2) routine electronic medical records; (3) dried blood spots; and (4) IDI with participants randomized to the intervention condition. The collection of data will be conducted by (1) a fieldworker; (2) the project manager; (3) lab-based researcher; and (4) a qualitative interviewer, respectively. Procedures for data collection (regardless of source) will be outlined in SOPs. We have a bank of well-developed SOPs that our group has developed for previous studies. All data management will take place at UCT following procedures established by our group for multiple previous studies.

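### The plan explores effect modification by comparing effects within subgroups and specifies no arm-by-factor interaction; if read from separate subgroup p-values, 43 women would often give a false contrast

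*Combined protocol and SAP*

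**What the plan says.** Section 9 (Analytic considerations), under Data analysis, sets out generalized estimating equations (GEE) for self-reported adherence, engagement in care and viral suppression, adjusted for baseline adherence and any baseline demographic imbalance. On model terms it says "Intervention condition, time of assessment, and condition*time interaction will be entered as model effects". The only text on effect modification follows shortly after: "If there is evidence of an intervention effect we will explore factors that may modify intervention effects", and then "we will compare intervention effects within subgroups of women based on key demographic clinical and psychosocial characteristics".

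The plan does not say what counts as evidence of an effect, which characteristics are the key ones, where they would be cut, how the subgroup effects would be compared, or how several factors would be handled.

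The Protocol Summary gives the size of the trial as "62 participants consented; 43 randomized". The power statement in section 9 rests on a larger number: "With a sample size of 60, between two groups, 2 follow-up measurements, controlling for self-reported baseline adherence". The same section describes the pilot as exploratory.

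**The concern.** An effect that is significant in one subgroup and not in another is not evidence that the two effects differ. In subgroups of about 21 women, that pattern will be common even when the true effect is identical. The usual protection is to estimate the difference between the subgroup effects directly, as an interaction. The authors wrote out an interaction with time but none with a modifier.

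The pilot is meant to support a larger trial, so a false contrast could influence which moderators or which women that trial concentrates on. This is a possibility and not something the protocol states: the source it names for choosing future mediators and moderators is the in-depth interviews (section 7, Aim 3 Qualitative Component). The table of measures in section 7 also offers many candidate factors (sociodemographics, pregnancy intentions, disclosure, partner violence, depression, substance use, self-efficacy and others), so the number of contrasts could be large.

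**Working it through.** **Inputs from the documents.** 43 randomized (Protocol Summary); 1:1 allocation (section 7, Randomization); effects of d = 0.3, 0.5 and 0.8 and a 0.05 level (section 9); at least 80% retention at 6 months, anticipated in section 9 for the interview sample, which would leave about 0.80 × 43 = 34 women.

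**Assumptions not in the documents.** Two subgroups, the same true effect in both, a normal outcome compared by t-test, two-sided testing, and modification declared when exactly one subgroup has p<0.05.

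**1. The plan's own figures.** The documents give power, not a false-contrast rate. For 60 women at d = 0.3, 0.5 and 0.8 they state 29%, 65% and 98%. A plain two-sided t-test with 30 per arm gives 21%, 48% and 86%; one-sided gives 31%, 61% and 92%. Averaging two follow-ups correlated at r = 0.30 multiplies the variance by (1 + 0.30)/2 = 0.65 and gives 29%, 66% and 97%. The stated figures are therefore plausible, but they cannot be confirmed because no correlation is given. Only the values of d are carried forward.

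**2. Power within one subgroup.** With 43/4 = 10.75 women per arm per subgroup, the noncentrality is d × √(10.75/2), that is 0.70, 1.16 and 1.85. Against a critical t of 2.09, power p is about 10%, 20% and 42%.

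**3. Exactly one subgroup significant.** The chance is 2p(1 − p):

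- d = 0.3: 2 × 0.10 × 0.90 = 18%
- d = 0.5: 2 × 0.20 × 0.80 = 32%
- d = 0.8: 2 × 0.42 × 0.58 = 49%

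**4. With the overall-effect condition.** If evidence means overall p<0.05, simulation with cells of 11, 11, 10 and 11 women gives about 62%, 63% and 60%. The rate rises because the condition mostly removes trials in which neither subgroup is significant.

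**5. Interaction test on the same simulated data.** False-positive rate about 5% at every d, with or without the overall condition.

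**6. Sensitivity (percent with exactly one subgroup significant, d = 0.3 / 0.5 / 0.8).**

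| Setting | No condition | Given overall p<0.05 |
|---|---|---|
| 43 women, equal subgroups | 18 / 32 / 49 | 62 / 63 / 60 |
| 34 women, equal subgroups | 16 / 27 / 45 | about 60 to 62 throughout |
| 43 women, variance × 0.66 | 23 / 40 / 49 | 64 / 63 / 53 |
| 43 women, 70:30 split | 18 / 32 / 53 | 66 / 67 / 66 |

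**7. What the interaction can show.** With 80% power and two-sided 5%, the detectable main effect is 2.80 × √(4/43) = 0.85 SD. The detectable interaction is 2.80 × √(16/43) = 1.71 SD. For k independent factors tested unadjusted, the chance of at least one false interaction is 1 − 0.95^k: 14% for three, 23% for five and 40% for ten.

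**The case against.** The strongest reply is that the plan never says modification will be judged from separate p-values. Comparing effects across subgroups is what an interaction estimate does, and nothing in the sentence excludes one. The stated purpose of the pilot is to obtain an effect size and its direction, which favours estimates over significance labels. This stands. A reader might infer that the authors chose subgroup p-values over an interaction test; the text does not show that. What it shows is that within-subgroup effects are the only method named and that no arm-by-factor term is specified.

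A reader might also take about one half as the ceiling on the false-contrast rate in a trial this small. That is not supported. One half is the maximum of 2p(1 − p) for two equal subgroups at any sample size; in 43 women it needs d of about 0.89. At the protocol's small and moderate effects the unconditional rate is 18% and 32%. Nor is it a limit, since the overall-effect condition or unequal subgroups can push the rate above one half.

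Two further points stand. The calculation is a t-test on a normal outcome, whereas the plan uses GEE and two of its three efficacy outcomes (retention and suppression) are binary. And an interaction test has little power here, so it is not a cure. The exploratory label lowers the stakes, but it does not supply a method for comparing the subgroup effects.

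**Conclusion.** The concern holds in a conditional form. Section 9 plans to compare effects within subgroups after evidence of an overall effect, and specifies no condition-by-moderator interaction. If the comparison were made on separate p-values, a common true effect would look like a difference about 18% to 49% of the time over d = 0.3 to 0.8, and about 60% to 63% if overall p<0.05 is required first, against about 5% per factor for an interaction test. These rates rest on 43 women, two equal subgroups, a normal outcome and no attrition. They should not be carried over to the binary outcomes. The consequence is small in an openly exploratory pilot, but a better method is available on data already being collected.

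**What to change.** Replace the subgroup sentence in section 9 with wording such as: *Effect modification will be explored by adding an arm-by-factor term (for the effect at 6 months postpartum) to the outcome GEE, for a short list of factors fixed before outcomes are examined by arm; the interaction estimate and 95% CI will be reported, without within-subgroup p-values, and labelled exploratory.*

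Two details need care. The model already contains condition by time, so the text must say which visit the term refers to. The timing should be tied to the first look at outcomes by arm and not to unblinding, because participants learn their allocation at enrolment and only the interviewers are masked.

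The cost is one sentence and the choice of a few factors; no new data, visits or participants are needed. The plan should state the limits alongside it: the interaction will be imprecise, and testing several factors unadjusted still raises the chance of a false finding, which is why the list should be short.
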